3.4.2 Safety Endpoints

Safety measurements are described in protocol Section 4.2.1 – Rationale for Endpoints and Section 8.3 – Safety Assessments. Safety and tolerability will be assessed by clinical review of all relevant parameters including AEs, AEs leading to discontinuation, SAEs, fatal AEs, laboratory values and vital signs.

3.4.3 Patient-Reported Outcome Endpoints

The PRO instruments in this study are the EORTC QLQ-C30 and EuroQol-5D (EQ-5D). The EQ-5D will provide data for use in economic models and analyses including developing health utilities or quality-adjusted life years (QALYs). The following PRO endpoints will be assessed.

- Mean change from baseline in EORTC QLQ-C30 global health status/quality of life scores and physical functioning score at pre-specified timepoint (see definition in section [3.6.3.2](#))
- Mean change from baseline in EQ-5D-5L visual analogue scale (VAS) at pre-specified timepoint

The EORTC QLQ-C30 global health status/quality of life scores and physical functioning score will also be assessed by:

- **Overall improvement**

Improvement is defined as a 10-point or more increase in score (in the positive direction) from baseline at any time during the study and confirmed by a 10-point or more improvement at a visit scheduled at least 6 weeks later (Osoba et al., 1998 [1], King 1996 [2]).

- **Overall improvement/stability**

Stability is defined as, when the criteria for improvement are not met, a less than 10 points worsening in score from baseline at any time during the study and confirmed by a less than 10 points worsening at a visit scheduled at least 6 weeks later.

Overall improvement/stability is defined as the composite of improvement and stability.

The definition of improvement as a change of 10 points or greater from baseline is per Osoba et al. (1998) [1] and King (1996) [2]. Changes from baseline in EORTC QLQ-C30 scores will also be interpreted according to recent subscale-specific guidelines, which indicate that clinically meaningful differences vary by scale (Cocks et al., 2012).

- **Deterioration**

Deterioration is defined as, greater than 10 points worsening in score from baseline at any time during the study.

3.5 Analysis Populations

3.5.1 Efficacy Analysis Populations

For Part 1, the intention-to-treat (ITT) population will serve as the population for primary efficacy analyses. All randomized participants will be included in this population. Participants will be included in the treatment group to which they are randomized.

For Part 2, participants who are eligible to receive retreatment with pembrolizumab according to the criteria in protocol Section 6.7 will serve as the population for efficacy analyses. Details on the approach to handling missing data are provided in Section 3.6 – Statistical Methods.

3.5.2 Safety Analysis Populations

The All Participants as Treated (APaT) population will be used for the analysis of safety data. The APaT population in Part 1 consists of all randomized participants who received at least one dose of study treatment in Part 1. Similarly, the APaT population in Part 2 consists of all Part 2 participants who received at least one dose of study treatment in Part 2.

For part 1, participants will be included in the treatment group corresponding to the study treatment they actually received for the analysis of safety data using the APaT population. For most participants this will be the treatment group to which they are randomized. Participants who take incorrect study treatment for the entire treatment period will be included in the treatment group corresponding to the study treatment actually received. Any participant who receives the incorrect study treatment for one cycle, but receives the correct treatment for all other cycles, will be analyzed according to the randomized treatment group and a narrative will be provided for any events that occur during the cycle for which the participant is incorrectly dosed.

In Part 1 (Part 2), at least one laboratory or vital sign measurement obtained subsequent to at least one dose of study treatment of Part 1 (Part 2) is required for inclusion in the analysis of each specific parameter in Part 1 (Part 2). To assess change from baseline in Part 1 (Part 2), a baseline measurement in Part 1 (Part 2) is also required. See baseline definitions in section 3.6.4 of this document.

3.5.3 PRO Analysis Populations

PRO analyses are based on the PRO Full Analysis Set (FAS) population, defined as all randomized participants who have at least one PRO assessment available for the specific endpoint and have received at least one dose of study intervention. Participants will be analyzed in the treatment group to which they are randomized.

3.6 Statistical Methods

3.6.1 Statistical Methods for Efficacy Analyses

Statistical testing and inference for safety analyses are described in Section 3.6.2. Efficacy results that will be deemed to be statistically significant after consideration of the Type I error control strategy are described in Section 3.8, Multiplicity. Nominal p-values will be computed for other efficacy analyses, but should be interpreted with caution due to potential issues of multiplicity. For efficacy endpoints associated with Part 2, only descriptive summary statistics will be provided. The summary will be done separately by the randomized treatment group in Part 1.

The stratification factors used for randomization (see protocol Section 6.3.1.1 - Stratification) will be applied to all stratified analyses, in particular, the stratified log-rank test, stratified Cox model, and stratified Miettinen and Nurminen method [3]. In the event that there are small strata, for the purpose of analysis, strata will be combined to ensure sufficient number of participants, responses and events in each stratum. Due to the small number of pediatric participants enrolled (2 participants), stratum 1 (pediatric participants) will be combined with other strata according to the T-stage level. This is applicable to all stratified analyses throughout this sSAP.

For analyses of DMFS, OS, TTST and PRFS2, follow-up will continue whether or not participants go from Part 1 to Part 2, i.e. for Participants go from Part 1 to Part 2 and have first event in Part 2, their event date or the date of the last assessment date in Part 2 (censoring date if no documented event at the time of the analysis) will be used for analysis.

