Participants assigned in the Part 1 initial treatment phase to the placebo arm who experience recurrence at any point during Part 1 therapy and follow-up and meet all crossover criteria will be offered crossover to pembrolizumab per dosing criteria in Section 4.3. Participants on the pembrolizumab arm during the initial phase of treatment who are greater than 6 months from last dose of pembrolizumab treatment and who experience a recurrence will be offered rechallenge with pembrolizumab per dosing criteria outlined in Section 4.3. Participants who have local recurrence, including local metastatic lymph nodes or distant metastases that are surgically resected may receive up to 17 cycles of therapy with pembrolizumab and participants with an unresectable local (regional metastatic lymph nodes, in-transit, satellite, and/or microsatellite metastases) or an unresectable distant recurrence may receive up to 35 cycles of therapy with pembrolizumab per Section 1.3.2.

All participants should have screening imaging within 28 days prior to C1D1 in Part 2 Crossover/Rechallenge phase. The Part 1 EOT scan can be used as baseline for Part 2 if done within 4 weeks of 1st dose in Part 2. Participants who have had surgical resection of lesion

captured on imaging must have a scan after surgery or radiation is complete to establish baseline imaging within 4 weeks prior to start of Part 2 therapy. Brain MRI must be obtained within 4 weeks prior to start of Part 2 treatment, unless contradicted; then CT may be acquired.

Disease recurrence/progression is confirmed by investigator (radiographically and/or by exam with subsequent biopsy) and RECIST 1.1/iRECIST will be used to identify disease progression in participants with metastatic/unresectable disease identified at the start of Part 2 therapy. Local recurrence should be documented with photo image.

Radiotherapy (palliative or adjuvant) is allowed prior to Part 2 (eg, post lymph node dissection radiotherapy when indicated). Radiotherapy has to be completed prior to first dose and complete wound healing is required prior to first dose. Radiotherapy is allowed during treatment in Part 2 as palliative therapy (treatment of pain, impending fracture, etc.) in participants with unresectable recurrence or metastatic disease. If surgery or radiotherapy other than described above is indicated while on Part 2 therapy Sponsor must be consulted.

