All eligibility criteria from Part 1 Sections 5.1 and 5.2 remain valid and must be reconfirmed prior to enrollment into Part 2 of the study with the EXCEPTION of:

- Inclusion Criteria 2, 3, 4 and 5
- Exclusion Criteria 5, 6 and 11

Participants must also meet the following requirements for entry into Part 2:

- Participant must have experienced an investigator determined/confirmed disease recurrence radiographically and/or by exam with subsequent biopsy. Local recurrence must be documented with photo image. Participants will only be eligible for Part 2 treatment after the first recurrence. If a participant experiences a second recurrence, they will not be eligible for Part 2. Participants who are less than 6 months from their last Part 1 pembrolizumab dose at the time of recurrence are not eligible for Part 2 treatment.

Note: Cutaneous lesions and other superficial lesions detectable only by physical exam must be categorized as nontarget lesions for Part 2 of the study.

- No new anticancer treatment was administered after the last dose of Part 1 study treatment.
- Participant is continuing from Part 1 and has completed 17 cycles of pembrolizumab or any number of cycles with placebo with no delays in treatment  $\geq 12$  weeks. If a  $\geq 12$ -week treatment delay has occurred, Sponsor approval must be obtained before moving into Part 2 of the study.

Note: For any participant who is not able to complete the required 17 cycles of pembrolizumab or have  $\geq 12$ -week treatment delay on placebo arm, a notification to the Sponsor is required to determine if it would impact their eligibility for entry into Part 2.

- Surgical resection or biopsy of unresectable or metastatic disease completed within 4 weeks of first dose.

- Full resection of lesions or biopsy of unresectable or metastatic disease confirmed by site pathologist to be melanoma.

Note: If biopsy is clinically contraindicated, investigators should seek Sponsor review and approval to start participant on Part 2 therapy.

If participant is identified to have a thoracic lesion or lymph node suspicious for a recurrence (especially if solitary lesion), it is encouraged that a biopsy be performed to confirm metastatic melanoma versus another lung primary malignancy versus a nonmalignant lung disease (eg, sarcoidosis).

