#### **8.11.3.4 Survival Follow-up Contacts**

Part 1 participants with distant metastases will move into Survival Follow-up if they do not qualify for or choose to not enter Part 2 of the study. Part 2 participants with a history of distant metastases or who develop new distant metastases during Part 2 will move into Survival Follow-up.

Participant Survival Follow-up status will be assessed approximately every 12 weeks until death, withdrawal of consent, or the end of the study, whichever occurs first. The collection of survival includes disease status (recurrence, progression, or new malignancy) if available or not already collected in imaging scans; record of further anticancer therapies and the outcomes in accordance with local regulations and participant consent.

The first Survival Follow-up assessment should be scheduled as described below:

- For participants who discontinue treatment intervention and who will not enter the efficacy follow-up phase, the first Survival Follow-up contact will be scheduled 12 weeks after the discontinuation visit and/or Safety Follow-up visit (whichever is last).
- For participants who completed assessments in Efficacy Follow-up, the first Survival Follow-up contact will be scheduled 12 weeks after the last Efficacy Follow-up visit has been performed.

These participants should be assessed or contacted by telephone or at an in-person visit approximately every 12 weeks to review disease status, recent imaging, and current therapy. Site investigator must collect and review copy of imaging reports, photographs, and pathology reports (including imaging and biopsy/pathology assessment done external to site) to update disease status if it is available. A central imaging vendor will be used to collect, clean, and hold submitted tumor imaging obtained during the SFU phase of the study. In the event that a participant refuses any further contact, or if a participant is discontinued from the study, the participant can authorize their site investigator to provide updated information about their tumor, anticancer treatment, well-being, and overall status updates on their behalf.

Radiographic imaging in Survival Follow-up may be performed as clinically indicated, per local standard of care, or following new anticancer therapy imaging schedule. Information regarding poststudy anticancer treatment will be collected if new treatment is initiated.

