#### **9.6.1.3 Overall Survival**

The nonparametric Kaplan-Meier method will be used to estimate the survival curves. The treatment difference in survival will be assessed by the stratified log-rank test. A stratified Cox proportional hazard model with Efron’s method of tie handling will be used to assess the magnitude of the treatment difference (the HR). The HR and its 95% CI from the stratified Cox model with a single treatment covariate will be reported. The stratification factors used for randomization (see Section 6.3.1.1 – Stratification) will be applied, as stratification factors used for analysis, to both the stratified log-rank test and the stratified Cox model. Kaplan-Meier estimates and the corresponding 95% CIs at specific follow-up time points will be provided for OS. Participants without documented death at the time of the analysis will be censored at the date of the last follow-up.

Additional supportive unstratified analyses may also be provided. Further details of OS sensitivity analyses will be described in the sSAP as needed.

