3.6.1.3 Overall Survival (OS)

The non-parametric Kaplan-Meier method will be used to estimate the survival curves. The treatment difference in survival will be assessed by the stratified log-rank test. A stratified Cox proportional hazard model with Efron’s method of tie handling will be used to assess the magnitude of the treatment difference (the HR). The HR and its 95% CI from the stratified Cox model with a single treatment covariate will be reported. The stratification factors used for randomization (See protocol Section 6.3.1.1 – Stratification) will be applied to both the stratified log-rank test and the stratified Cox model. Kaplan-Meier estimates and the

corresponding 95% CIs at specific follow-up time-points will be provided for OS. Participants without documented death at the time of the analysis will be censored at the date of the participant was last known to be alive.

Additional supportive unstratified analyses may also be provided.

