3.6.1.9 Analysis Strategy for Key Efficacy Endpoints

Table 4 summarizes the primary analysis approach for primary and key secondary efficacy endpoints. Sensitivity analysis methods are described above for each endpoint as applicable.

Table 4 Efficacy Analysis Methods for Key Efficacy Endpoints

Endpoint/Variable (Description, Time Point)	Statistical Method [†]	Analysis Population	Missing Data Approach
Primary Hypothesis 1			
RFS	Test: Stratified log-rank test Estimation: Stratified Cox model with Efron's tie handling method	ITT	See Table 1 for censoring rules
Secondary Hypothesis 2			
DMFS	Test: Stratified log-rank test Estimation: Stratified Cox model with Efron's tie handling method	ITT	Censored at last disease evaluation
Secondary Hypothesis 3			
OS	Test: Stratified log-rank test Estimation: Stratified Cox model with Efron's tie handling method	ITT	Censored at last known alive date
[†] Statistical models are described in further details in the text. For stratified analyses, the stratification factors used for randomization will be used as stratification factors for analysis.			

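### sSAP 3.6.1 gives OS a second censoring date for Part 2 entrants: harmless if it means last contact, tilted toward pembrolizumab if programmed as last disease assessment

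*SAP*

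**What the plan says.** sSAP 3.6.1 has one sentence for four endpoints. It begins "For analyses of DMFS, OS, TTST and PRFS2, follow-up will continue whether or not participants go from Part 1 to Part 2" and then says which date to use for people who moved to Part 2: the event date or, failing that, "the date of the last assessment date in Part 2 (censoring date if no documented event at the time of the analysis". OS is named in the sentence, and *assessment* is not defined.

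The OS rule is worded differently elsewhere:

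- sSAP 3.6.1.3: participants without a documented death "will be censored at the date of the participant was last known to be alive".
- sSAP Table 4 (3.6.1.9): "Censored at last known alive date". Protocol Table 9 has the same rule.
- Protocol 9.6.1.3, text: participants without a documented death "will be censored at the date of the last follow-up", a third wording.

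Access to Part 2 differs by arm. Protocol 6.7 offers crossover to those on the "placebo arm who experience recurrence at any point during Part 1 therapy and follow-up", after any number of cycles, if the other criteria are met. On the pembrolizumab arm 17 completed cycles are normally required, and those "less than 6 months from their last Part 1 pembrolizumab dose at the time of recurrence are not eligible for Part 2".

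Protocol 8.11.3.4 adds that "Part 2 participants with a history of distant metastases or who develop new distant metastases during Part 2 will move into Survival Follow-up", where status is checked about every 12 weeks until death.

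**The concern.** The three endpoints listed beside OS are all censored at the last disease assessment (sSAP 3.6.1.2, 3.6.1.4 and 3.6.1.5). A programmer who applies one rule to all four could use that date for OS too. Under protocol 8.2.1.2, scheduled scans stop at Part 2 progression or on entry to DMFS or Survival Follow-up, whereas survival contacts can go on for years. A participant who dies after the last scan would count as a death; one who is alive just as long after the last scan would be cut off at that scan. This overstates the hazard after Part 2 entry. Because the entry rules put more such people in the placebo arm, the placebo hazard rises more.

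OS is a confirmatory endpoint under one-sided 2.5% control (sSAP 3.8), so its censoring date should not be open to choice at the first OS analysis, planned at about month 120.

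**Working it through.** **1. The plan's own OS figures.** Inputs from sSAP 3.8.3 and 3.9: 954 participants allocated 1:1, HR 0.67, 154 then 204 events, bounds Z = 2.3249 and 2.0138, control OS 75% at 120 months, 16 months' accrual, 4.7% annual dropout.

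- Mean of Z at look k is √(d_k/4) × ln(1/0.67): √38.5 × 0.4005 = 2.485 and √51 × 0.4005 = 2.860.
- Fixed design: Φ(2.860 − 1.960) = 0.816.
- Two looks, correlation √(154/204) = 0.869: power = 1 − P(Z1 < 2.3249 and Z2 < 2.0138) = 0.809. The plan states 0.8050. Null crossing is 0.0100 at the interim and 0.0250 overall, as stated.
- Control hazard λ = −ln(0.75)/120 = 0.00240 per month. With dropout δ, the death probability for entry at month a is λ/(λ+δ) × [1 − exp(−(λ+δ)(T − a))], averaged over a from 0 to 16 and summed over arms with 0.67λ on pembrolizumab. This gives 155-156 deaths at month 120 and 204-205 at month 180, against 154 and 204 stated.

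The OS design is therefore reproduced.

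**2. Both censoring rules on the same data.** I simulated 954 participants, 1,500 runs per scenario. Recurrence follows the plan's RFS cure model (50% long term, 68% at 60 months on control). Death after recurrence is calibrated to 75% control OS at 120 months. Part 2 entry follows the arm-specific rules in protocol 6.7. Deaths count in full under both rules; only the censoring date of living Part 2 entrants differs. The analysis is an unstratified log-rank test and Cox model, with rejection at one-sided Z = 1.96 at a single look.

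Assumed, because the documents do not say: 30-60% of eligible placebo and 20-60% of eligible pembrolizumab recurrences enter Part 2; 70% complete 17 cycles; background mortality is 1% per year. Living Part 2 entrants per run number 27-64 on placebo and 6-30 on pembrolizumab.

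| Meaning of last assessment in Part 2 | Fall in OS HR | Type I error |
|---|---|---|
| Includes 12-weekly survival contacts | at most 0.002 | unchanged |
| Lags last contact by up to 12 months | 0.002-0.010 | up by at most 0.003 |
| Disease assessments stop at progression (median 24 or 60 months after recurrence) | 0.011-0.059 | 0.029-0.061 |

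With last-known-alive censoring for everyone and no true effect, the HR averages 0.99-1.01 and rejection is 0.019-0.033 (Monte Carlo standard error about 0.004). No scenario moved away from pembrolizumab.

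**3. Examples at month 180, assessments stopping at progression (median 24 months).**

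| Scenario | Uptake, placebo / pembrolizumab | HR, last known alive | HR, last disease assessment | Rejection |
|---|---|---|---|---|
| No effect | 60% / 20% | 1.004 | 0.945 | 0.023 to 0.059 |
| RFS HR 0.60 | 60% / 20% | 0.760 | 0.713 | 0.51 to 0.70 |
| RFS HR 0.60 | 60% / 60% | 0.759 | 0.721 | 0.52 to 0.66 |
| RFS HR 0.60 | 30% / 30% | 0.762 | 0.743 | 0.50 to 0.58 |

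The shift remains with equal uptake, so it does not depend on assuming lower uptake on pembrolizumab. In all three RFS HR 0.60 rows the average HR goes from above to below the plan's final bound of 0.7538. The simulated death counts (about 241 with no effect, 216 with RFS HR 0.60) differ from the planned 204, so that comparison is only a guide.

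**The case against.** The strongest reply is that the plan already settles the matter. The sSAP introduction leaves the principal features of the confirmatory analyses to the protocol, and protocol Section 9 requires a protocol amendment to change the methods for key secondary hypotheses. Protocol Table 9 says last known alive, and sSAP 3.6.1.3 and Table 4 repeat it. The shared sentence exists to extend follow-up through Part 2, not to shorten it. It also omits the word *disease*, which the sSAP includes where it means a disease assessment. Survival Follow-up is a column of the Part 2 schedule of activities, so survival contacts can count as Part 2 assessments.

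All of this stands. A reader might infer that the sSAP does censor OS at the last scan and that OS is therefore biased toward pembrolizumab. The documents do not support that: it needs the general sentence to override the OS-specific rule and *assessment* to take its narrower meaning.

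It may also be said that the biased result comes from a mixed reading, which counts deaths after the last scan but ignores contacts after it. The text does not require that reading. But OS is death from any cause (sSAP 3.4.1.2), so no program would drop those deaths. Taking the censoring date from disease assessments would produce exactly this mixture.

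Finally, OS is tested only after RFS and DMFS succeed. The 3-6% is thus the error of the OS comparison taken alone at one look, not a familywise rate. That limit is accepted.

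What remains is that OS is named in a sentence whose censoring date differs from its own rule.

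**Conclusion.** The censoring rule for OS is inconsistent as written, with low severity. The likely reading does no harm: if survival contacts count, or the OS-specific rule governs, the HR changes by at most 0.002. Harm is conditional on programming the shared sentence as a last disease assessment. The direction is then toward pembrolizumab and follows from the entry rules in protocol 6.7. The illustrative size is an HR lower by about 0.01-0.06 and a one-sided type I error of about 3-6% for the OS test.

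The direction is well founded. The size is not fixed by the documents, which give no expected Part 2 uptake by arm and no time from Part 2 entry to last assessment. The planned 154 and 204 events and the 80% power are unaffected.

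**What to change.** In sSAP 3.6.1, remove OS from the censoring clause. Alternatively, add that OS is censored at the date last known alive from any source, including Survival Follow-up and vital-status contacts, whether or not the participant entered Part 2. In the same edit, say what *assessment* means for DMFS, TTST and PRFS2. At the next protocol amendment, align the last-follow-up wording in 9.6.1.3 with Table 9.

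The cost is one sentence in the sSAP and one phrase in the protocol, to be made before the first OS analysis. Data collection, event targets, boundaries and power stay as they are.
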